[H2a] Perceived CVD and diabetes risks, perceived life expectancies and subjective survival probabilities are correlated with objective risks predicted from risk factors, including demographics, BMI etc.

Test:

- Regress perceived personal risks from both information treatment group and control group on 10year CVD risk predicted from Globorisk, 10-year diabetes risk predicted from Finnish Diabetes Risk Score (FINDRISC) (Lindstrom and Tuomilehto 2003) and lifetable survival probabilities.³
- Data from section D prior to treatment group receiving information on personal CVD risk.

[H2b] Perceived CVD and diabetes risks, and perceived life expectancies, deviate from predicted risks due to differential weighting of risk factors.

Test:

- Regress perceived personal risks of both information treatment group and control group (section D) on risk factors and compare coefficients with those obtained from regression of predicted probabilities on risk factors. For example, for personal 10-year CVD risk, compare coefficients from model of reported probability to those used in Globorisk risk prediction tool to produce predicted probabilities. Moreover, compare other coefficients to those found in previous literature on the determinants of CVD and diabetes risks, and on life expectancies, such as, family history and exercise.
- Regress perceived personal CVD and diabetes risks, life expectancies and subjective survival probabilities (section D) on the respective perceived base rates (section B) and on risk factors to test the extent to which perceived personal risks are based on perceived base rates with an adjustment to make use of information available to the respondent on risk factors.

[H2c] Perceived base rates for CVD, diabetes, life expectancy and survival probability are higher than objective (predicted) base rates.

Tests:

- Compute mean deviations of perceived base rates (section B) from predicted base rates. A positive (negative) mean deviation hints at overestimation (underestimation) of CVD prevalence/diabetes prevalence/life expectancy/survival probability.
- Compute mean ratios of perceived base rates to objective (predicted) base rates. A mean ratio > 1 (< 1) hints at overestimation (underestimation) of CVD prevalence/diabetes prevalence/life expectancy/survival probability.
- Compare proportion of sample with perceived base rate < objective (predicted) base rate with proportion with perceived base rate > objective base rate.

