³ This test could be conducted using all survey respondents, including those in the lottery intervention arm. The reason we exclude the latter is because later tests make use of the information intervention and we want to have a consistent sample throughout.

[H2d] The accuracy of base rate estimates varies with education, personal risks, life expectancies and survival probabilities, the respondent's confidence in the accuracy of his perceived base rate, the respondent's degree of worry about CVDs, the respondent's degree of dispositional optimism, and possibly other characteristics.

Tests:

- Repeat computation of mean deviations and mean ratios as explained in [H2c] for each gender/age category combination and check whether CVD/diabetes prevalence, life expectancy and survival probabilities are systematically (by factors defined in [H2d]) over- or underestimated.
- Regress mean square estimation error ((perceived predicted)²) and binary indicator of whether base rate has been over- or underestimated on education level, predicted personal CVD/diabetes risk, predicted life expectancies and survival probabilities, confidence about own base rate estimates, worry about CVDs, dispositional optimism, and possibly other characteristics.

[H2e] Perceived personal CVD risk is negatively correlated with perceived life expectancies and survival probabilities.

- Regress perceived personal CVD risk on perceived life expectancies and on survival probabilities until the age of 80 years (section D).
- Compute fraction of respondents who state a perceived life expectancy conditional on experiencing a CVD event lower than their unconditional perceived life expectancy.

[H2f] Perceived personal CVD and diabetes risks, life expectancies and subjective survival probabilities deviate systematically from base rates with a tendency towards optimism bias.

Tests:

- Compute mean deviations of prior perceived personal risk (section D) from predicted base rate for treatment and control group. A negative mean deviation is consistent with optimism bias.
- Compare the mean deviation of the treatment group that is given information on the base rate (section C) with the control group that is not. Establish the extent to which under-/over-estimation of the base rate contributes to apparent optimism/pessimism bias.
- Compute mean ratio of perceived personal risk to predicted base rate for treatment and control group. A mean ratio < 1 is consistent with optimism bias.

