- Compare proportion of sample with perceived personal risk < base rate with proportion with perceived personal risk > base rate for treatment and control group. This does not suffer from the same sensitivity to outliers as the two measures proposed immediately above.
- Repeat the mean deviation test for an event with positive valence and similar average risk as 10year CVD risk. For this we use the probability of living past the age of 80 (section D). A positive mean deviation in this case would be consistent with pessimism bias. If we find this, then we cannot conclude that positive mean deviation in previous test is indicative of optimism bias.

- Test whether control group individuals state lower perceived personal risks (section D) than perceived base rates (section B) given not provided with base rate information.
- Compute share of unrealistically optimistic, accurate and unrealistically pessimistic individuals according to the definitions of Radcliffe and Klein (2002). Test whether there are significantly more unrealistically optimistic than unrealistically pessimistic individuals.
 - In particular, compute the ratio of predicted personal CVD risk to predicted CVD base rate (Globorisk), as well as the ratio of perceived personal CVD risk (section D) to perceived CVD base rate (section B). Individuals who provide a perceived risk ratio of more than 10% lower than their predicted risk ratio are defined as unrealistically optimistic. Likewise, individuals who consider themselves to be at higher relative risk than their predicted risk ratio (by more than 10%) are considered unrealistically pessimistic. Individuals whose perceived relative risk is within 10% of their predicted risk ratio are considered accurate.
 - Since a ratio is affected more by noise at small values than at large values, we will also define optimism / pessimism in terms of the difference between perceived personal and base rate CVD risk in comparison with the difference in the respective predicted risks.

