- Compute difference between perceived unconditional personal CVD risk and perceived conditional personal CVD risk for both control and treatment groups and regress on variables that indicate the respondents' smoking status, BMI and systolic blood pressure level. Test whether higher risk factor levels are associated with a higher difference between perceived unconditional and conditional CVD risks.

Q3: Do beliefs about susceptibility to CVD respond to information on predicted personal CVD risk?

[H3a] Beliefs about personal susceptibility to CVD are updated to incorporate information provided on objective CVD risk predicted from risk factor exposure.

Test:

- We test whether beliefs are updated consistently with Bayes rule such that,
 - posterior_i = $\lambda \cdot predicted_i + (1 \lambda) \cdot prior_i$ where $\lambda \in [0,1]$ is an updating weight representing the individual's willingness to abandon her own prior in favor of the provided risk information. To estimate λ for the 10-year personal CVD risk, we estimate:

$$(posterior_i - prior_i) = \lambda(predicted_i - prior_i) + \varepsilon_i, \qquad (3.1)$$

where the *prior* is perceived personal CVD risks of the information treatment group before being told their predicted risk obtained from Globorisk (D_T), posterior is the equivalent after being told the predicted risk (F_T) and the predicted is the Globorisk prediction of personal CVD risk. This yields an estimate of the extent of updating following the provision of only personal CVD risk information. $\hat{\lambda} = 1$ indicates complete revision of beliefs in which there is 100% reliance on the new information in the prediction and the prior to completely dismissed. $\hat{\lambda} = 0$ indicates no updating of beliefs. $\hat{\lambda} \in (0,1)$ indicates some updating, which can still be consistent with Bayes. For example, the respondent may weigh the new information and the prior in relation to the perceived sample size from which each is obtained.

• To test the response of risk perceptions to the different types of information provided, we estimate regressions of the general form: $p_i = \beta x_i + \gamma I_i + u_i$, where I_i is a dummy variable indicating whether a respondent has been allocated to the information treatment or to the control group and the interpretation of γ varies according to the definition of the dependent variable as follows:

Dependent variable (p)	Effect identified

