UPecon survey												Х	Х		
monitoring															
Survey firm delivers														Х	
follow-up data															
Analysis of follow-up data														Х	Х
Write papers															\rightarrow

Our intention is to field the baseline survey in August-September 2017. As explained above, the information intervention will form part of the risk perceptions module of the baseline survey. The module used with information treatment group respondents will differ from that used with the lottery treatment group and the control group. The module will be positioned in the survey after physical measurements of blood pressure and BMI in order that these measures can be used in the calculation of the predicted CVD risk that will be revealed to the treatment group respondents.

Those allocated to the lottery intervention will be told of their chance to enter the lottery at the end of the baseline survey and given a voucher to be exchanged for a lottery ticket at a specific RHU/CHC. The chance to enter the lottery expires one month after the baseline in order that we observe a sufficiently long period between risk assessment at the designated facility and the follow-up survey.

The follow-up will be conducted around 6-7 months after the baseline in March-April 2018. This will provide sufficient time to observe the effect of medications prescribed at initial contact with the RHU/CHC and to assess whether follow-up consultations are conducted for the target populations, as stipulated by the PhilPEN protocol.

7. Outcomes

We will estimate effects on predicted CVD risk, risk factors, health care management of CVD, CVD-related behaviours, perceptions of CVD risk and knowledge of CVD risk factors.

Principal outcome

The principal outcome for both interventions is mean 10-year risk of a heart attack or stroke predicted using the office version of Globorisk (Udea et al 2017).

i) Mean 10-year risk of CVD event (Globorisk prediction)

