A conformé letter of agreement will be sent to the mayor of every municipality or city from which barangays and households will be sampled. The letter contains information about the study, its objectives, proponents and funding source, and study activities (surveys and interventions) that will be undertaken. Additionally, the letter solicits the support and permission of the mayor to engage the local rural health unit/city health center in the lottery intervention. The tasks and responsibilities of the participating RHU/CHC are also laid out in an accompanying sheet. The letter assures the mayor that participation in the survey and interventions is voluntary, and informed consent of the participants will be sought first before the interview and participation in the intervention. Assurance will be given that participation of RHU/CHC will not generate any added cost to the local government, and that the study team will provide the lottery prize and take charge of delivering the prize money to the winner. The mayor will indicate his support and permission by signing the conformé.

13. Ethical issues

Data protection

To track respondents at follow-up, records of their names and addresses will need to be kept. These records will be kept on a secure computer in encrypted files accessible only by specified members of the immediate study team. Files containing names and addresses will not be shared by anyone outside of the study team. When data are made available to other researchers, respondents will be distinguished only by unique identification numbers and no names and addresses will be included in the data files.

Blood pressure information

Blood pressure will be measured using a digital monitor following standard procedures. It can be anticipated that some participants will have an elevated blood pressure reading that may warrant preventive actions. We will adopt the following protocol for dealing with elevated blood pressure readings:

- $140/90 \text{ mmHg} \le BP < 180/120 \text{ mmHg}$: Tell the respondent of the likelihood of hypertension, and advise to see a physician for confirmation. The information and advice will be recorded on an orange coloured card given to the respondent. Proceed with the interview.
- BP \geq 180/120 mmHG: Advise the respondent to proceed immediately to the nearest health facility. Issue a red coloured card with this advice. Stop the interview.

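### For BP 140/90 to below 180/120, stated personal risk (section D) appears to follow the survey's own hypertension warning, and H2a, H2b and H2f make no allowance for it

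*Combined protocol and SAP*

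**What the plan says.** - **Order of the interview.** Section 6 says of the risk perceptions module: "The module will be positioned in the survey after physical measurements of blood pressure and BMI".
- **The warning.** Section 13 (Blood pressure information) sets the rule for 140/90 to below 180/120: "Tell the respondent of the likelihood of hypertension, and advise to see a physician for confirmation". An orange card is issued and the interview goes on. At 180/120 or above the interview stops.
- **Who is told.** The rule is not limited to one arm. Section 13 also says that the lottery arm hears of a high reading and that controls are told their measurements. It does not say when controls are told.
- **Status of section D.** Section 4 treats the personal risk stated there as the prior belief. H3a defines the prior as belief "before being told their predicted risk obtained from Globorisk".
- **Use of section D.** H2a relates it to predicted risk and describes the data as "Data from section D prior to treatment group receiving information on personal CVD risk". H2b regresses it on risk factors, partly to see how far respondents "make use of information available to the respondent on risk factors". H2f subtracts the predicted base rate and states: "A negative mean deviation is consistent with optimism bias". H2f also classifies individuals: "Individuals who provide a perceived risk ratio of more than 10% lower than their predicted risk ratio are defined as unrealistically optimistic".
- **Allowance for the warning.** The text contains no adjustment, exclusion or sensitivity analysis for warned respondents.

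**The concern.** The first objective is to learn how far people lack information about their own CVD risk. Undiagnosed hypertension is a main example of that gap. The warning reaches just these people, apparently shortly before their belief is recorded.

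Two readings are exposed. First, in H2a and H2b, part of the association between blood pressure and stated risk may have been supplied by the survey. It then does not show what respondents knew beforehand. Second, in H2f, if the warning raises stated risk, the deviation from the base rate moves upward in warned respondents and their optimism is understated.

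**Working it through.** **Plan's own figure.** Two-sided 5%, 80% power, effect 0.2 × 0.6 = 0.12 SD gives 1,091 per arm. Times 1 + 9 × 0.1 = 1.9, times 1 − 0.36 = 0.64, this is 1,327, against 1,306 in Table 6 for mean CVD risk (1.6% apart). The sample size is not in dispute. The check shows that the design effect used below is the plan's.

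**Inputs.** Table 5: undiagnosed hypertension 0.20; systolic BP of 140 or more 0.31; on BP medication 0.10; mean CVD risk 11.35. Table 4: ineligible 0.14, ICC 0.1 or 0.05, cluster size 10. Table 6 (binary outcomes): information 299, control 1,361, together 1,660. These are follow-up sizes. Section D is asked at baseline, where allowing for 10% attrition gives 1,660/0.9 = 1,844.

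**Newly informed share.** It is 0.20 if ineligibility is unrelated to being undiagnosed, and 0.20/0.86 = 0.233 if no undiagnosed person is ineligible. That is 332 to 386 of 1,660, or 369 to 429 of 1,844. Both are slightly high, because interviews stop at 180/120.

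**Effect of an assumed shift of s points in stated risk.**

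| s | Rise in mean section D (0.20s to 0.233s) | Rise in high- versus normal-BP contrast (0.65s to 0.95s) |
|---|---|---|
| 0 | 0 | 0 |
| 5 | 1.0–1.2 | 3.2–4.8 |
| 10 | 2.0–2.3 | 6.5–9.5 |

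The contrast factors are 0.20/0.31 = 0.65 (no medicated person at 140 or above) and 0.20/(0.31 − 0.10) = 0.95 (all of them). They are approximate: 0.20 uses the 140/90 rule and 0.31 is systolic only.

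For scale, the standard error of mean section D is SD × √(1.9/1,660). An assumed SD of 15 to 25 gives 0.51 to 0.85 points. A 5-point shift could therefore mask modest optimism.

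**H2f's 10% rule.** The accurate band is 2 × 0.10 × predicted ratio × perceived base rate. For ratios of 1.0 to 2.0 it is 2.3–4.5 points wide at a base rate of 11.35, 4–8 at 20 and 6–12 at 30 (base rates assumed). Small shifts reclassify only respondents near an edge.

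**Cost of a repeat below 140/90.** Enrolled respondents at or above 140/90 range from 0.20 (every diagnosed person medicated and excluded) to 0.31/0.86 = 0.36. A share k of 0.80 to 0.64 remains. The standard error of a mean or an arm contrast changes by √{[1 + (10k − 1)ICC]/k ÷ [1 + 9 ICC]}:

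| | k = 0.80 | k = 0.64 |
|---|---|---|
| ICC 0.1 | 1.058 | 1.126 |
| ICC 0.05 | 1.079 | 1.170 |

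A regression slope loses more, because the predictor's range narrows. For a slope on systolic BP itself (normal, mean 125.61, SD one seventh of the mean, clustering ignored) the ratio is about 1.48. H2a's predictor is total predicted risk, of which BP is only one input, so this is a guide only.

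**H5b.** The bias is the excess share of warned respondents in the at-or-below group times the card's effect on behaviour. Globorisk also contains BP, so warned respondents have higher predicted risk, which pushes them the other way. I simulated this with assumed values: stated risk mean 15, SD 15; predicted risk mean 10, SD 2.3, higher by 2 to 6 points if warned; 20% to 36% warned. The excess is −6 to −1 points with no shift, −1 to +3 with a 5-point shift and +2 to +6 with a 10-point shift. An assumed card effect of 10 percentage points then gives at most 0.06 × 0.10, or 0.6 points either way, against the 6 to 10 point binary differences in Table 5.

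**The case against.** The plan never claims that section D is untouched by the survey. Its prior is defined relative to the Globorisk figure, and in the information arm section D already follows base-rate information. Q2 asks whether beliefs incorporate risk information, and a reading just announced is information available to the respondent. This stands: the plan does not misdefine its prior. What remains is interpretive. A gradient partly created minutes earlier does not describe what this population knew.

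The repeat also cannot isolate the card. Selecting on BP selects on an input to predicted risk, and respondents below 140/90 may have heard a reassuring reading before section D. This stands too. The repeat is a sensitivity analysis, and a different result would not prove a card effect.

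The order and the card's timing may be settled in the baseline questionnaire (Appendix C), which is not in the text. That is why the point says appears.

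A reader might infer more, in two ways:

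- **That H5b would mistake a card effect for reduced ambiguity.** The documents do not support a direction. Predicted risk rises with BP as well, so the imbalance can go either way and is likely small. For the CVD risk outcome, the regression also conditions on baseline predicted risk.
- **That the trial's main results are biased.** They are not. Section 5.2 says that only the risk perceptions module differs between arms, and the card rule is the same in all. The principal outcome, H5a, H6 and the randomised comparison of treated posterior with control section D are unaffected. In equation (3.1) and H3d, prior and posterior both follow the card.

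**Conclusion.** The point holds for H2a, H2b and H2f as a limit on interpretation that the plan should address. It rests on the inferred order and on Table 5 planning values from a national survey of ages 40–69. The size of the belief shift is an assumption throughout. Section 3.1 itself notes that bad news may be filtered out, so it could be near zero. An upward shift of 5 to 10 points would raise mean stated risk by 1.0 to 2.3 points and the high-BP contrast by 3.2 to 9.5 points. No direction is claimed for H5b. The improvement is worthwhile and cheap, and it concerns the descriptive belief results only.

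**What to change.** 1. Pre-specify repeats of H2a and H2f in respondents below 140/90 in both arms. Report them beside the full-sample estimates with confidence intervals, and do not judge them on significance alone.
2. Describe section D in carded respondents as belief after BP notification.
3. Do not read the H2b high-BP coefficient as knowledge held before the survey. The repeat cannot test that contrast, because it has no respondents with high BP.
4. Record when in the interview the card and the measurement results are given, in every arm. If the questionnaire already fixes this, say so.
5. A below-140/90 repeat of H5b is optional.

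The cost is one timing field and two extra analyses on BP already measured. The interview order, the consent form and the ethics approval stay as they are, and the planned analyses lose nothing. The repeats use about 64% to 80% of respondents. The standard error of a mean is about 6% to 17% larger, and that of the H2a slope somewhat more. The population also differs, and this should be stated with the results.

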Appendix A – Prescribed treatments under PhilPEN

The PhilPEN operations manual (Department of Health, 2012b), following the WHO protocol for the integrated management of diabetes and hypertension, stipulates that the prescribed treatment response depends on both assessment of individual risk factors and the total 10-year risk of a CVD event predicted using the WHO/ISH charts, as follows:

- 1) Individual risk factors:
 - a. All with BP \geq 160/100 mmHg to be given antihypertensive treatments.
 - b. All with stable CVD or diabetes continue with prescribed treatment and considered to have CVD risk>30% (see below).
 - c. All with total cholesterol ≥ 8 mmol to be given lifestyle advice and statins.
 - d. All with diabetes to be given Metaformin (if blood glucose high despite diabetic diet), given a statin if \geq 40 and resources sufficient, given advice on foot care, referred for eye examination every 2 years, and followed-up every 3 months.
- 2) CVD risk <20%:
 - a. Counsel on diet, physical exercise and smoking cessation.
 - b. If risk <10%, follow-up after 12 months.
 - c. If risk 10- <20%, follow-up after 3 months until meet targets, and then 6-9 months.
- 3) CVD risk 20% <30%
 - a. Counsel on diet, physical exercise and smoking cessation.
 - b. If BP \geq 140/90 (in DM \geq 130/80), to be given low dose of an antihypertensive, betablocker or calcium channel blocker (Hydrochlorthiazide, Enalapril, Atenelol or Amlodipine).
- 4) CVD risk \geq 30%
 - a. Counsel on diet, physical exercise and smoking cessation.
 - b. If BP \geq 130/80, to be given one of Thiazide, ACE inhibitor, beta-blocker or calcium channel blocker.
 - c. To be given a statin.
 - d. Followed-up every 3 months.

	Mean CVD risk	Mean systolic BP in mm Hg	Mean BMI	Mean waist circumference in cm	Binary outcomes
Required sample sizes					
Info treatment per round (unadjusted)	220	226	220	226	232
Lottery treatment per round (unadjusted)	1,000	1,028	1,000	1,028	1,056
Control per round (unadjusted)	1,000	1,028	1,000	1,028	1,056
Total baseline sample (adjusted)	3,687	3,790	3,687	3,790	3,894
Total follow-up sample	2,220	2,282	2,220	2,282	2,344
Number of clusters	222	229	222	229	235
Avg. cluster size at baseline	16.61	16.55	16.61	16.55	16.57
Estimated costs in					
PHP					
Total cost	10,642,249	10,904,744	10,642,249	10,904,744	11,164,135

Appendix B – Sample size calculations – Sensitivity analysis Table B1 Results of power calculations and cost estimations – Scenario 2

	Mean CVD risk	Mean systolic BP in mm Hg	Mean BMI	Mean waist circumference in cm	Binary outcomes
Required sample sizes					
Info treatment per round (unadjusted)	269	274	269	274	280
Lottery treatment per round (unadjusted)	1,880	1,920	1,880	1,920	1,960
Control per round (unadjusted)	1,880	1,920	1,880	1,920	1,960
Total baseline sample (adjusted)	6,693	6,834	6,693	6,834	6,977
Total follow-up sample	4,029	4,114	4,029	4,114	4,200
Number of clusters	403	412	403	412	420
Avg. cluster size at baseline	16.61	16.59	16.61	16.59	16.61
Estimated costs in					
РНР					
Total cost	18,434,482	18,803,017	18,434,482	18,803,017	19,173,026

Table B2 Results of power calculations and cost estimations – Scenario 3

Table B3 Results of power calculations and cost estimations - Scenario 4

	Mean CVD risk	Mean systolic BP in mm Hg	Mean BMI	Mean waist circumference in cm	Binary outcomes
Required sample sizes					
Info treatment per round (unadjusted)	206	211	206	211	217
Lottery treatment per round (unadjusted)	1,440	1,480	1,440	1,480	1,520
Control per round (unadjusted)	1,440	1,480	1,440	1,480	1,520
Total baseline sample (adjusted)	5,126	5,267	5,126	5,267	5,410
Total follow-up sample	3,086	3,171	3,086	3,171	3,257
Number of clusters	309	318	309	318	326
Avg. cluster size at baseline	16.59	16.56	16.59	16.56	16.60
Estimated costs in					
РНР					
Total cost	14,369,292	14,737,016	14,369,292	14,737,016	15,107,025

	Mean CVD risk	Mean systolic BP in mm Hg	Mean BMI	Mean waist circumference in cm	Binary outcomes
Required sample sizes					
Info treatment per round (unadjusted)	378	378	378	384	390
Lottery treatment per round (unadjusted)	1,722	1,722	1,722	1,750	1,778
Control per round (unadjusted)	1,722	1,722	1,722	1,750	1,778
Total baseline sample (adjusted)	6,349	6,349	6,349	6,451	6,554
Total follow-up sample	3,822	3,822	3,822	3,884	3,946
Number of clusters	383	383	383	389	395
Avg. cluster size at	16.58	16.58	16.58	16.58	16.59
baseline					
Estimated costs in					
PHP					
Total cost	17,513,807	17,513,807	17,513,807	18,038,748	18,038,748

Table B4 Results of power calculations and cost estimations – Scenario 5

